4.6.3. Randomization, Adaptation, and Masking

4.6.3.1. Randomization

The randomization unit for these trials will be the CSI. Each CSI includes a catchment area of approximately 10 communities.

CSIs will be randomized in a 2:1 allocation favoring azithromycin to the following 2 arms:

- **Programmatic azithro 1–11:** all children aged 1–11 months will be offered a biannual dose of azithromycin. This distribution will be provided by existing community health workers as part of the Ministry of Health's community health program.
- **Programmatic no intervention:** All children aged 1–11 months will not receive azithromycin within the framework of this study. However, all children in this study will receive other health services provided by community health workers as part of the Ministry of Health's community health program.

4.6.3.2. Adaptation

The randomization sequence will be generated by the trial biostatistician at UCSF

The Programmatic Trial will use an adaptive allocation modeled after the adaptive allocation employed in the Mortality/Resistance Trial. Communities will undergo the first randomization in a 2:1 allocation favoring the Programmatic azithro 1–11 arm. If the program continues after the first year, new communities will be enrolled using the same adaptation methods used for the Mortality Trial.

After the Mortality Trial's primary outcome analysis, the study team and key stakeholders will determine whether the Programmatic Trial continues. If the study continues, the Mortality Trial communities will be included in the Programmatic Trial and additional regions will be added over time (Figure 2). In this platform design, additional treatment arms may be added to the trial or arms may be dropped from the trial based on additional information from other studies, updates to the WHO guidelines, or preferences of programs or policymakers in Niger. With such

changes, protocol details, power calculations, and analysis plans will be updated accordingly in the protocol and statistical analysis plan.

Refer to the trial's Statistical Analysis Plan (SAP) for complete details of the adaptive randomization algorithm.

4.6.3.3. Masking

In the Programmatic Trial, participants, and implementers will not be actively masked from the study arm allocation given that no placebo will be used. Outcome assessors and data analysts will be masked.

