In Delivery Trial II, 80 communities will be randomized in a 1:1 allocation to one of two arms: 1) **delivery azithro 1–11**: biannual oral azithromycin administration to children aged 1–11 months distributed by community health workers or 2) **delivery azithro 1–59**: biannual oral azithromycin administration to children aged 1–59 months distributed by community health workers. Costs and coverage will be compared across age-based strategies.

In the Programmatic Trial, CSIs will be randomized in a 2:1 allocation to one of two arms favoring the programmatic azithro 1–11 arm: 1) **programmatic azithro 1–11**: biannual oral azithromycin administration to children aged 1–11 months distributed by community health workers or 2) **no intervention**: no distribution of azithromycin. Approximately 1,500 communities from 150 CSIs will be included. All communities still receive routine health services offered by community health workers working for the Niger Ministry of Health's community health program. Antimicrobial resistance will be monitored using cluster sampling from a subset of 20 eligible CSIs per arm (40 CSIs total). Sampling will take place within communities as well as CSIs. Mortality will be monitored through birth history surveys. All infectious cause and cause-specific clinic visits will be monitored through routine CSI data collection.

Primary Outcomes

Mortality/Resistance Trial

- Mortality rate (deaths per 1,000 person-years at risk) among children 1–59 months of age at 2.5 years from the first enrollment, comparing the azithro 1–59 and placebo arms
- Mortality rate (deaths per 1,000 person-years at risk) among children 1–11 months of age at 2.5 years from the first enrollment, comparing the azithro 1–11 and placebo arms
- Mortality rate (deaths per 1,000 person-years at risk) among children 12–59 months of age at 2.5 years from the first enrollment, comparing the azithro 1–11 and azithro 1–59 arms

Prevalence of genetic determinants of resistance to macrolides from nasopharyngeal swabs in children 1–59 months old after 2 years of distributions

- Load of genetic determinants of resistance to macrolides from rectal swabs in children 1–59 months old after 2 years of distributions

Delivery Trial I

- Treatment coverage as defined by the number of doses recorded by the community health workers and eligible population captured during the post-distribution census

Delivery Trial II

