4.6.4. Outcomes

4.6.4.1. Primary Outcomes*

- Number of infectious cause CSI visits per month for children aged 1–59 months over 1 year
- Number of cause-specific CSI visits (diarrhea, respiratory infections, and malaria) per

month for children 1–59 months of age over 1 year

*If the Programmatic Trial continues, outcomes will be assessed every 2 years

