4.6.8.4. Measurement of Clinic Visit Outcomes

Clinic visits will be monitored through passive surveillance at CSIs in Programmatic Trial study regions. All infectious cause visits and cause-specific visits for diagnoses of respiratory infection, diarrheal disease, and malaria will be recorded among children under 5 based on the age groups routinely reported in Niger. Visits will be measured continuously by CSI staff using Niger’s DHIS2 national system for health information database. Records will be regularly reviewed for eligible entries and data including child age, community of residence, date of visit,

diagnosis at visit, and treatment given will be extracted electronically.

The presence of respiratory infection, diarrheal disease, and malaria are determined using the UNICEF Integrated Management of Childhood Illness flowchart currently used in Niger. A copy of this Integrated Management of Childhood Illness flowchart can be found in the Section 7.12 of the appendix.

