### Trial masking

The Mortality/Resistance trial is a double-masked, placebo controlled trial. All participants are masked to their treatment. Study investigators and field staff are masked to treatment with the

exception of the unmasked portion of the trial analysis team at UCSF. The unmasked portion of the analysis team will conduct the response adaptive allocation and pre-specified interim analyses. Unmasked members include one of the four PIs for the trial ([name]), one of the two biostatisticians for the trial ([name]), and one analyst ([name]). These members were designated in January 2022 before any adaptation or interim analyses would commence. The rationale for including this composition of the unmasked analysis team was to ensure sufficient statistical and subject matter expertise to guide the critical interim discussions and decisions for the response-adaptive trial, in coordination with the trial's Data and Safety Monitoring Committee.

The Delivery Trials and Programmatic Trial are unmasked and do not include a placebo.

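### The Programmatic Trial's statement that outcome assessors are masked does not hold for its clinic-visit outcomes, which staff of the randomized health centres record in an open trial

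*Protocol*

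**What the plan says.** Protocol section 4.6.3.3 (Programmatic Trial, Masking) first says that "participants, and implementers will not be actively masked from the study arm allocation given that no placebo will be used". It then adds: "Outcome assessors and data analysts will be masked". It does not say who the outcome assessors are.

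The other relevant statements are:

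- **Unit and allocation.** Section 4.6.3.1: "The randomization unit for these trials will be the CSI", and "CSIs will be randomized in a 2:1 allocation favoring azithromycin to the following 2 arms". Section 1.2: "Approximately 1,500 communities from 150 CSIs will be included".
- **Primary outcomes.** Section 4.6.4.1 lists two, both clinic-visit counts. The first is "Number of infectious cause CSI visits per month for children aged 1–59 months over 1 year"; the second is the cause-specific counts for diarrhea, respiratory infection and malaria. Section 1.2 also lists two laboratory resistance outcomes as primary, which section 4.6.4.2 lists as secondary.
- **Who records visits.** Section 4.6.8.4: "Visits will be measured continuously by CSI staff", in the national DHIS2 system under passive surveillance. The three named diagnoses follow the Integrated Management of Childhood Illness (IMCI) flowchart. Records are then extracted electronically.
- **SAP.** Section 2, Trial masking: "The Delivery Trials and Programmatic Trial are unmasked and do not include a placebo".

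**The concern.** In a trial without placebo, masked outcome assessment is the main remaining protection against arm-dependent measurement. A reader of section 4.6.3.3 would credit the clinic-visit result with that protection. Yet the count is produced inside the randomized unit, by its own staff, before any extractor or analyst sees it.

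If staff in azithromycin CSIs label or log visits differently because they know the drug is being given, the visit ratio moves with no drug effect. Recruiting more CSIs does not reduce such a bias. At stake is how the clinic-visit result may be read: as a masked measurement, or as a routine count from an open trial that needs supporting checks.

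**Working it through.** **Step 1. Follow the clinic-visit count from origin to analysis.**

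| Stage | Who acts | Can it be masked as described? |
|---|---|---|
| Attendance | Caregivers; community health workers also refer children (4.6.3.4) | No. Both groups are openly unmasked (4.6.3.3) |
| Diagnosis and recording | CSI staff for recording (4.6.8.4); their role in diagnosis is implied by the IMCI text, not stated | No means of concealment described |
| Extraction from DHIS2 | Not named | Yes, in principle |
| Analysis | Data analysts | Yes |

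Masking the last two stages cannot correct a difference introduced at the second.

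**Step 2. Do CSI staff know the arm?** No section says so directly. The indications are:

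- The CSI is the unit randomized, and its catchment either has open distribution or does not (4.6.3.1).
- Approval is sought before activities begin in any community or CSI (4.6.6).
- CSI-based sampling excludes children already given study treatment (4.6.2), so at the 40 sampled CSIs someone must establish treatment status.
- Section 6.6 describes CSI-employed agents delivering treatment in the related Delivery Trial.

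Knowledge of the arm is therefore a likely inference, not a documented fact.

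**Step 3. Compare the sister trial.** For the Delivery Trial, section 4.5.3.3 says that outcome assessors, like participants and implementers, are not actively masked, and claims masking for analysts only. The Protocol thus already has wording that fits open ascertainment.

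**Step 4. Size, by illustration only.** These documents give no power, variance or effect size for the Programmatic Trial, so there is no planned figure to reproduce. The number of CSIs is consistent: 1,500 communities / about 10 per CSI = 150, which at 2:1 is 100 and 50.

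Assume no drug effect, recording lower by a fraction r in one arm, a z-test on CSI-level log visit rates, two-sided alpha 0.05, and a between-CSI coefficient of variation CV:

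- SE = CV × √(1/100 + 1/50) = CV × 0.1732
- d = |ln(1 − r)|
- P(significant) = Φ(d/SE − 1.96) + Φ(−d/SE − 1.96)

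For CV = 0.3 and r = 5%: SE = 0.0520, d = 0.0513 and d/SE = 0.987. So P = Φ(−0.973) + Φ(−2.947) = 0.165 + 0.002 = 0.167.

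| Assumed CV | r = 5% | r = 10% | r = 20% |
|---|---|---|---|
| 0.2 | 32% | 86% | 100% |
| 0.3 | 17% | 53% | 99% |
| 0.4 | 12% | 33% | 90% |
| 0.5 | 9% | 23% | 73% |

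Both r and CV are assumptions; the nominal rate is 5%.

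**Step 5. Dilution cuts both ways.** Only ages 1–11 months are treated, but the count covers 1–59 months. Protocol section 2 gives five times as many older as younger children in MORDOR I–Niger. If visits follow population (an assumption), infants make 1/6 of visits.

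- *Signal.* A true 20% fall in infants lowers the whole count by 20% × 1/6 = 3.3%. If infants make 1/3 of visits, it is 20% × 1/3 = 6.7%. A 5% recording shift is of the same order.
- *Bias.* If altered coding were confined to treated-age infants, a 5% overall shift would need 5% ÷ 1/6 = 30% of their infectious visits relabelled, and a 10% shift 60%. At 1/3 of visits, the figures are 15% and 30%. Large shifts by that route alone are less plausible.

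**The case against.** The strongest case against has five parts.

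- **Undefined term.** Section 4.6.3.3 may mean laboratory readers, record extractors or birth-history interviewers, and for some of these it can be true. This stands, and it limits the point to clinic visits. It does not rescue the sentence for those outcomes, because masking later handlers leaves recording open.
- **Staff knowledge of the arm is not documented.** This stands. A reader might infer that the documents say CSI staff know the arm; they do not. Community health workers are named as distributors and CSI staff as recorders.
- **The SAP does not contradict the Protocol.** A reader might take the SAP's word for the whole trial as ruling out masked assessors. It is better read as shorthand: the same sentence calls the Delivery Trials unmasked, although Protocol 4.5.3.3 masks their analysts.
- **Attendance changes are not plainly bias.** Open participation is disclosed. In a comparison of programme delivery with usual care, altered care-seeking may be part of the programme's effect. This stands: whether it is bias depends on the estimand, which these sections do not state.
- **The governing plan was not supplied.** SAP section 2 says that a separate SAP covers the Programmatic Trial, and it may already contain negative controls or completeness checks. This stands for the added analysis. It would not make the wording of 4.6.3.3 accurate.

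The IMCI flowchart also constrains classification of the three named causes. It does not govern whether visits are logged completely.

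**Conclusion.** The point holds for the clinic-visit outcomes, the only primary outcomes in section 4.6.4.1. As described, they are recorded by staff of the randomized CSIs in an open trial, and masking of assessors cannot be claimed for them. It can be claimed for laboratory readers, record extractors and analysts. That includes the resistance outcomes, whose rank as primary or secondary differs between sections 1.2 and 4.6.4.2. A reader might infer that no primary outcome has masked assessment; the listing in section 1.2 does not support that.

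Differential recording or coding could bias the visit ratio in either direction by an unknown amount. The percentages above show sensitivity under assumed shifts and variances; they do not estimate actual bias. The conclusion rests on the likely inference that CSI staff know their arm. The open design is a legitimate programmatic choice; the fault is in claiming a safeguard that the described procedures do not provide for these outcomes.

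**What to change.** 1. **Wording.** In Protocol 4.6.3.3, state that clinic-visit outcomes are ascertained unmasked, following the approach of 4.5.3.3. Limit masked assessment to laboratory outcomes, record extraction and analysis.
2. **Supportive check.** Where the DHIS2 extract permits, and unless the separate Programmatic SAP already does so, add a by-arm comparison of non-infectious visits (or all-cause minus infectious) at 1–59 months as a negative control. A general shift in attendance or recording would appear in it; relabelling from infectious to non-infectious would appear as an opposite movement. It would miss infection-specific changes in care-seeking, so it is a partial check and should be described as such.

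The wording costs one protocol edit. The comparison looks feasible: section 4.6.8.4 extracts the diagnosis at each visit, and SAP section 3.5.1 plans all-cause CSI visits for the Mortality Trial. The documents do not confirm that non-infectious counts are available for this age range, so that should be checked first. If they are, the cost is an additional tabulation of routine records.

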4.6.3.4. Interventions

In the Programmatic Trial, existing community health workers employed by the Minister of Health will be utilized. Community health workers from randomly selected, eligible communities will be trained to distribute azithromycin to children 1–11 months of age from within randomly selected CSIs every 6 months for a period of 1 year, with distributions potentially continuing beyond 1 year dependent on funding.

In all communities in the Programmatic Trial, community health workers will continue to distribute routine care services, including prevention, screening, and treatment of diseases (such as malnutrition, malaria, diarrhea, and pneumonia), referral to the health center, nutritional advice, vaccination, or administration of vitamin A, as per the Ministry of Health community health program.

Please refer to Section 4.4.3.4 for more details on the intervention.

4.6.3.5. Dosage Information

Please refer to Section 4.5.3.5.

4.6.3.6. Side Effects

Please refer to Section 4.4.3.6.

4.6.3.7. Study Medication Storage and Accountability

Please refer to Section 4.4.3.7.

4.6.3.8. Medication Quality Control

Please refer to Section 4.4.3.8.

4.6.4. Outcomes

4.6.4.1. Primary Outcomes*

- Number of infectious cause CSI visits per month for children aged 1–59 months over 1 year
- Number of cause-specific CSI visits (diarrhea, respiratory infections, and malaria) per

month for children 1–59 months of age over 1 year

*If the Programmatic Trial continues, outcomes will be assessed every 2 years

4.6.4.2. Secondary Outcomes

- Prevalence of genetic determinants of macrolide resistance in nasopharyngeal swabs in children aged 1–59 months from population-based samples after 2 years of distribution
- Load of genetic determinants of macrolide resistance in rectal swabs among children aged 1–59 months from population-based samples after 2 years of distribution
- Prevalence of genetic determinants of macrolide resistance in nasopharyngeal swabs in children aged 1–59 months with respiratory illness from CSI-based samples after 2 years of distribution
- Load of genetic determinants of macrolide resistance in rectal swabs among children aged 1–59 months with diarrheal disease from CSI-based samples after 2 years of distribution
- Infant- and under-5 mortality rate (deaths per 1,000 livebirths) 2 years after the first treatment as assessed via birth history

Program costs as captured by routine administrative data collection during the study period and by micro-costing activities

- Estimated national-scale effects (health and cost) of scaling up each strategy. Other implementation outcomes defined in the Proctor Outcomes Framework,¹³ including feasibility and acceptability, as captured during routine administrative and monitoring data collection during the study period and by stakeholder interviews at the participant, community, and health system levels after one round of distributions (Table 3)
- Treatment coverage as defined by projections using national and study census data collection as well as satellite imagery

Microbiome outcomes for rectal swab collections

- Gamma diversity, estimated as the alpha diversity of the pooled community sample using the Shannon diversity index
- Overall microbial structure using Manhattan distance
- Relative abundance of individual microbial taxa at genus and species level

4.6.5. Sample size

4.6.5.1. Overview

Please refer to Section 4.4.5.1.

4.6.5.2. Sample Collections

In the Programmatic Trial, sample collection will take place in communities in the catchment area of 40 randomly selected CSIs (20 CSIs per arm) and at the same 40 selected CSIs themselves. Additional details about this collection can be found in Section 4.10.3, *Measurement of Sample Based Outcomes*.

In all communities selected for sample collections, treatment distribution for that round will be conducted after sample collections.

Refer to SAP for details of power calculations.

4.6.6. Recruitment

Before implementation begins in a region, a sensitization campaign will inform local health authorities and community leaders of the study design and nature of participation in the trial. In addition to IRB and national-, regional-, and district-level approval, community-level approval will be obtained before study activities begin in any community or CSI. All children aged 1–11 residing in a CSI catchment area randomized to receive treatment will be recruited for the intervention. Household-level consent will be obtained for the census activities, and caregiver/guardian consent will be obtained for interventions and sample collection. Details of informed consent are found in Section 5.3.

4.6.7. Adverse Events Monitoring

Please refer to Section 4.4.7.

4.6.8. Data Collection, Management, Analysis, and Monitoring

4.6.8.1. Data Collection Overview

Programmatic Trial data will be collected electronically and on paper as described below.

4.6.8.2. Measurement of Mortality Outcomes

For communities randomized to participate in the Programmatic Trial, mortality will be monitored through an annual door-to-door birth history survey in a subset of randomly selected communities using trained census workers and following similar methods as described above. All women aged 12–65 will be invited to participate and asked about the status of each live birth they experienced over the past 10 years, including the name, age, sex, date of birth, current status, and as needed, date of death.

4.6.8.3. Measurement of Sample Based Outcomes

In the Programmatic Trial, sample collection will take place within communities in the catchment area of 40 selected CSIs (20 CSIs per arm) and at the same 40 selected CSI locations.

- For samples collected within communities (population-based):
 - 3 communities per CSI from each of the 40 CSIs (120 communities total) will be randomly selected from the pool of eligible communities and followed to monitor antimicrobial resistance. In each community, 10 children aged 1–59 months will be selected to participate in nasopharyngeal and rectal swab sample collections. One rectal swab and one NP swab will be collected from each child.
- For samples collected at CSI locations (CSI-based):
 - 1 rectal swab will be collected from the first 30 children who present to the CSI with symptoms of diarrheal disease.
 - 2 nasopharyngeal swabs will be collected from the first 30 children who present to the CSI with symptoms of respiratory disease. The second nasopharyngeal swab collected will be sent to the CERMES lab for processing.

- 1 rectal swab and 2 nasopharyngeal swabs will be collected from the first 30 children who for routine medical care (e.g. vaccination) and present with no disease symptoms. The second nasopharyngeal swab collected will be sent to the CERMES lab for processing.

In the Programmatic Trial, population-based sample collections will follow similar procedures to those described above for the Mortality/Resistance Trial. CSI-based collections will take place in the same month as the community-based collections for that CSI, with a window of + or – 1 month. The presence of diarrheal or respiratory illness will be determined using the UNICEF Integrated Management of Childhood Illness flowchart currently used in Niger. Eligible children will be consecutively enrolled until the target sample sizes are achieved. A copy of the Integrated Management of Childhood Illness flowchart that will be used can be found in the Section 7.12 of the appendix.

To randomly select individuals for population-based monitoring in the Programmatic Trial, a “random walk” approach will be used.

Random walk selection protocol

1. Start at the home of the chef du village.
2. Use the application in CommCare to determine how many steps to go and in which direction to walk.
3. Approach the household that is closest to you when you finish your steps.
4. Ask the household if there are children 1-59 months of age and if the household is willing to participate. If not, choose the next closest household and repeat step 4.
5. Enter the number of eligible children 1-59 months in the household into the app, and use the app to select which child from which to take samples.
6. Take samples and complete data collection form.
7. Repeat steps 2-6 until you have completed 10 households.

For both trials with sample collections (the Mortality/Resistance Trial and Programmatic Trial), once the census is complete and the sample is generated, the study team will work with a local mobilizer to invite the sampled group to a central location in the community for sample collection. Samples will be collected by trained personnel and linked to census data through bar codes. Once sample collection is complete, the census team or community health workers will visit the study community to complete treatment for that round.

During collection, samples will be stored at ambient temperature or on ice at 4°C. At the end of each collection period, samples will be transported to a location near the sampled community with facilities to store samples at -20°C as required or directly to CRISP each day. At the end of the collection period, all samples will be transferred to a central storage location at CRISP in Niamey stored at -20°C as required until processed or shipped to UCSF for processing. Refer to Sample Collections Procedures and the Laboratory Procedures for full details.

